## **APPENDICES**

### **Appendix 1. Data Derivation details**

#### **Appendix 1.1. KCCQ (See protocol for a copy of the questionnaire)**

## **The Kansas City Cardiomyopathy Questionnaire Scoring Instructions**

There are 10 summary scores within the KCCQ, which are calculated as follows:

### **1. Physical Limitation**

- Code responses to each of Questions 1a-f as follows:

Extremely limited = 1  
Quite a bit limited = 2  
Moderately limited = 3  
Slightly limited = 4  
Not at all limited = 5  
Limited for other reasons or did not do = <missing value>

- If at least three of Questions 1a-f are not missing, then compute

Physical Limitation Score =  $100 * [(mean\ of\ Questions\ 1a-f\ actually\ answered) - 1] / 4$

*(see footnote at end of this document for explanation of meaning of "actually answered")*

### **2. Symptom Stability**

- Code the response to Question 2 as follows:

Much worse = 1  
Slightly worse = 2  
Not changed = 3  
Slightly better = 4  
Much better = 5  
I've had no symptoms over the last 2 weeks = 3

- If Question 2 is not missing, then compute

Symptom Stability Score =  $100 * [(Question\ 2) - 1] / 4$

### **3. Symptom Frequency**

- Code responses to Questions 3, 5, 7 and 9 as follows:

**Question 3**  
Every morning = 1  
3 or more times a week but not every day = 2  
1-2 times a week = 3  
Less than once a week = 4  
Never over the past 2 weeks = 5

### 3. Symptom Frequency (cont.)

#### Questions 5 and 7

All of the time = 1  
 Several times a day = 2  
 At least once a day = 3  
 3 or more times a week but not every day = 4  
 1-2 times a week = 5  
 Less than once a week = 6  
 Never over the past 2 weeks = 7

#### Question 9

Every night = 1  
 3 or more times a week but not every day = 2  
 1-2 times a week = 3  
 Less than once a week = 4  
 Never over the past 2 weeks = 5

- If at least two of Questions 3, 5, 7 and 9 are not missing, then compute:

$$\begin{aligned} S3 &= [(Question 3) - 1]/4 \\ S5 &= [(Question 5) - 1]/6 \\ S7 &= [(Question 7) - 1]/6 \\ S9 &= [(Question 9) - 1]/4 \end{aligned}$$

Symptom Frequency Score =  $100 * (\text{mean of } S3, S5, S7 \text{ and } S9)$

### 4. Symptom Burden

- Code responses to each of Questions 4, 6 and 8 as follows:

Extremely bothersome = 1  
 Quite a bit bothersome = 2  
 Moderately bothersome = 3  
 Slightly bothersome = 4  
 Not at all bothersome = 5  
 I've had no swelling/fatigue/shortness of breath = 5

- If at least one of Questions 4, 6 and 8 is not missing, then compute

Symptom Burden Score =  $100 * [(\text{mean of Questions 4, 6 and 8 actually answered}) - 1]/4$

### 5. Total Symptom Score

= mean of the following available summary scores:  
 Symptom Frequency Score  
 Symptom Burden Score

**6. Self-Efficacy**

- Code responses to Questions 10 and 11 as follows:

**Question 10**

Not at all sure = 1  
Not very sure = 2  
Somewhat sure = 3  
Mostly sure = 4  
Completely sure = 5

**Question 11**

Do not understand at all = 1  
Do not understand very well = 2  
Somewhat understand = 3  
Mostly understand = 4  
Completely understand = 5

- If at least one of Questions 10 and 11 is not missing, then compute

Self-Efficacy Score =  $100 * [(mean\ of\ Questions\ 10\ and\ 11\ actually\ answered) - 1] / 4$

**7. Quality of Life**

- Code responses to Questions 12, 13 and 14 as follows:

**Question 12**

It has extremely limited my enjoyment of life = 1  
It has limited my enjoyment of life quite a bit = 2  
It has moderately limited my enjoyment of life = 3  
It has slightly limited my enjoyment of life = 4  
It has not limited my enjoyment of life at all = 5

**Question 13**

Not at all satisfied = 1  
Mostly dissatisfied = 2  
Somewhat satisfied = 3  
Mostly satisfied = 4  
Completely satisfied = 5

**Question 14**

I felt that way all of the time = 1  
I felt that way most of the time = 2  
I occasionally felt that way = 3  
I rarely felt that way = 4  
I never felt that way = 5

#### 7. Quality of Life (cont.)

- If at least one of Questions 12, 13 and 14 is not missing, then compute

Quality of Life Score =  $100 * [(mean\ of\ Questions\ 12,\ 13\ and\ 14\ actually\ answered) - 1] / 4$

#### 8. Social Limitation

- Code responses to each of Questions 15a-d as follows:

Severely limited = 1  
 Limited quite a bit = 2  
 Moderately limited = 3  
 Slightly limited = 4  
 Did not limit at all = 5  
 Does not apply or did not do for other reasons = <*missing value*>

- If at least two of Questions 15a-d are not missing, then compute

Social Limitation Score =  $100 * [(mean\ of\ Questions\ 15a-d\ actually\ answered) - 1] / 4$

#### 9. Overall Summary Score

= mean of the following available summary scores:

Physical Limitation Score  
 Total Symptom Score  
 Quality of Life Score  
 Social Limitation Score

#### 10. Clinical Summary Score

= mean of the following available summary scores:

Physical Limitation Score  
 Total Symptom Score

Note: references to “means of questions actually answered” imply the following.

- If there are  $n$  questions in a scale, and the subject must answer  $m$  to score the scale, but the subject answers only  $n-i$ , where  $n-i \geq m$ , calculate the mean of those questions as  

$$(sum\ of\ the\ responses\ to\ those\ n-i\ questions) / (n-i)$$
  
 not  

$$(sum\ of\ the\ responses\ to\ those\ n-i\ questions) / n$$

If doing these calculations seems like too much trouble, consider using one of our tools – available at [www.cvoutcomes.org](http://www.cvoutcomes.org):

- SAS or SPSS code
- Excel spreadsheets
- Web data services

## Appendix 1.2. 6 Minute Walk Test Categorization

- a. Level 1: < 300 m
- b. Level 2: 300-374.9 m
- c. Level 3: 375-449.9 m
- d. Level 4:  $\geq 450$  m

The categories above represent increasing levels of ability.

To determine if a subject has improved, you would create a new variable/flag which would be based on the subtraction of [category at time 1] – [category at time 2].

e.g.: baseline category – visit 1 category

If this is negative, for example baseline = 2 and visit 1 = 3, thus  $2-3 = -1$ , then the subject would be indicated as improved.

If the subtraction is 0 then the subject is unchanged. And finally, if the subtraction is positive then the subject worsened.

### **Appendix 1.3. Calculation of QTc Interval Corrections**

**Fridericia's** heart rate correction formula:  $QTcF = QT / (RR)^{1/3}$  where  $RR = 60/HR$ ;  
**Bazett's** heart rate correction formula:  $QTcB = QT / (RR)^{1/2}$  where  $RR = 60/HR$ ;

### **Appendix 2. Definition and Use of Visit Windows in Reporting**

For the purpose of this study, Day 1 is defined as the first dose day under this protocol.

Day 1  $\pm$  1 week

Every other 3 month telephone visits between clinic visits  $\pm$  1 week

Clinic visits every 6 months  $\pm$  2 weeks

End of study visit  $\pm$  2 weeks

However, in order to maximize the use of all available data, the visit windows for each visit are expanded as follows:

Day 0: End of study visit from Fx1B-201

Day 1 + 1.5 months

Telephone contact (every 3 months between clinic visits)  $\pm$  1.5 months

Clinic visits (every 6 months)  $\pm$  3 months

End of study visit (see details below)

In the event that there is a break between the last visit of the parent study (Fx1B-201,) and the first day of dosing in the current study Fx1B-303 (B3461026); then the visit associated with the first day of enrollment in the current study Fx1B-303 (B3461026) will be the baseline visit of this study.

For an early termination visit within study B3461026 (Fx1B-303): The existing windowing rules will be used and as such, the data in the early termination visit should never replace an existing visit. If the visit covered by the windowing rules above is already populated with an existing visit, then the EOS visit should be mapped forward to the next clinic visit.

As an example, the EOS visit occurs at month 68.

If there is no month 66 visit, then the EOS visit becomes the month 66 visit.

If there is a month 66 visit, then the EOS visit becomes the month 78 visit.

For an unscheduled visit:

If possible, the existing windowing rules will be used, but the data should never replace an existing visit. If the visit is already populated, then the unscheduled visit should be mapped forward to the next appropriate visit for that measure if that visit is available.

As an example, the unscheduled visit occurs at month 68 and the data are collected annually.

If there is no month 66 visit, then the unscheduled visit becomes the month 66 visit.

If there is a month 66 visit, but no month 78 visit then the unscheduled visit becomes the month 78 visit.

If there are both month 66 and month 78 visits, then the unscheduled visit is not included in the summary analyses but is included in the listing as unscheduled.

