6.2. Study Period

6.2.1. Months 3, 9, 15, 21, 27, 33, 39, 45, 51, 57, 63, 69, 75, 81, 87, 93, 99, 105, 111, 117

Subjects will be contacted by telephone, contact is to be made \pm 1 week of scheduled time:

- Ask subjects non-leading questions such as “How do you feel?” and document adverse events.
- Record concomitant medications.
- Mail 3 month supplies of investigational product following telephone contact.
- These phone visits can be conducted in person at the clinic at the discretion of the sites.

6.2.2. Months 6, 12, 18, 24, 30, 36, 42, 48, 54, 60, 66, 72, 78, 84, 90, 96, 102, 108, 114

Subjects will return to the clinic for the following assessments. Visits are to occur \pm 2 weeks of the scheduled time:

- Conduct abbreviated physical examination, including weight and vital signs.

- Collect blood/urine samples for clinical laboratory assessments (section [7.3](#)).
- Perform Patient Global Assessment.
- Determine NYHA Classification.
- Administer Kansas City Cardiomyopathy Questionnaire.
- Conduct 6-minute walk test.
- Ask subjects non-leading questions such as “How do you feel?” and record adverse events.
- Record concomitant medications.
- Determine drug compliance and accountability.
- Dispense 3 month supply of investigational product.

6.2.3. Months 12, 24, 36, 48, 60, 72, 84, 96, 108

In addition to the above assessments, collect ECG and echocardiogram every 12 months.

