6.3. Subject Withdrawal

Subjects may withdraw from the study at any time at their own request, or they may be withdrawn at any time at the discretion of the investigator or sponsor for safety or behavioral reasons, or the inability of the subject to comply with the protocol required schedule of study visits or procedures at a given study site. In addition, the Sponsor may choose to discontinue this study, at which time all subjects will be withdrawn.

A subject may be withdrawn from the study for any of the following reasons:

- Withdrawal of consent;
- Adverse event;
- Protocol noncompliance;
- Subject lost to follow-up;
- Subject death.

Subjects who are prematurely withdrawn from the study will not be replaced. Subjects who discontinue from the study at any time following enrollment will have a final end of study visit performed, including all safety and efficacy assessments, at the time of discontinuation.

Upon regulatory approval of tafamidis for the treatment of TTR-CM in their respective country, and access to prescription tafamidis, subjects may be withdrawn from the study. The decision to withdraw subjects in a country will be done in consultation between the investigator and the sponsor. Subjects will have all end of study procedures completed prior to study withdrawal. These subjects are considered completers.

If a subject does not return for a scheduled visit, every effort should be made to contact the subject. In any circumstance, every effort should be made to document subject outcome, if possible. The investigator should inquire about the reason for withdrawal, request the subject to return all unused investigational product(s), request the subject to return for a final visit, if applicable, and follow-up with the subject regarding any unresolved adverse events (AEs).

If the subject withdraws from the study, and also withdraws consent for disclosure of future information, no further evaluations should be performed, and no additional data should be collected. The sponsor may retain and continue to use any data collected before such withdrawal of consent.

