## 7. HANDLING OF MISSING VALUES

Data which are based on entire scales which are missing will be analyzed as follows:

If the data are time until event data and there is no observed event (at any point during the trial) the observation will be censored at the last observation. If there was an observed event, the data associated with the first observation of that event will be used; all other observations will not be needed.

For all other data types, the data will be analyzed as follows: for analyses at each visit, the missing observations will not be used. Any visit after the subject was discontinued will remain as missing data.

For any subject missing a 12-month visit observation from Study Fx1B-201, if the Day 0 visit observation from the Fx1B-303 study is reported, the Day 0 visit observation from the Fx1B-303 will be imputed for the 12-month visit observation for Study Fx1B-201.

For specific scoring details, see [Appendix 1](#).

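### SAP Appendix 2 moves some end-of-study values to a clinic visit after discontinuation, which SAP Section 7 says stays missing

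*SAP*

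**What the plan says.** SAP Section 7 (Handling of Missing Values) states for data other than time-to-event data that "for analyses at each visit, the missing observations will not be used", and continues: "Any visit after the subject was discontinued will remain as missing data".

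SAP Appendix 2 first repeats the scheduled windows, including "Clinic visits every 6 months" with ±2 weeks. It then widens the clinic-visit window to ±3 months so that as much data as possible can be used. An early-termination visit follows these windows and may not overwrite an existing visit. If its slot is taken, "then the EOS visit should be mapped forward to the next clinic visit". The illustration begins "As an example, the EOS visit occurs at month 68" and ends "If there is a month 66 visit, then the EOS visit becomes the month 78 visit".

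Unscheduled visits are treated differently. They also move forward if the slot is taken, but if the later slot is taken too they go to the listing only.

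Protocol 6.3 says that subjects who discontinue "will have a final end of study visit performed, including all safety and efficacy assessments, at the time of discontinuation". Protocol 6.2.2 lists the clinic months, which include "54, 60, 66, 72, 78, 84, 90, 96".

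**The concern.** For a subject whose EOS visit falls in an already filled window, the two SAP sections prescribe different contents for the same cell. Section 7 leaves the next clinic visit blank, and Appendix 2 puts the EOS value there. Neither section is given precedence, so two programmers following the SAP could produce different tables from the same data.

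The affected outputs are the by-visit summaries, the shift tables (Patient Global Assessment, NYHA class, categorised 6-minute walk) and the MMRM estimates of change from baseline. These are the main efficacy output of a descriptive study with at most 35 subjects. Late rows will be small, so a single mislabelled record can be visible. A reader would take the row for a given month as measurements made around that month, on subjects still in the study.

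**Working it through.** **Inputs.** Clinic visits every 6 months (Protocol 6.2.2); annual ECG and echocardiogram visits at months 12, 24, … 60, 72, 84 … (Protocol 6.2.3); analysis window ±3 months (SAP Appendix 2); EOS visit at discontinuation (Protocol 6.3); mean 12-month 6-minute-walk change of −11 m in Fx1B-201 and −44 m in TRACS (Protocol 1.2.4).

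**1. The SAP's example does not reproduce.**
- Month 68 lies in the month-66 window: 66 − 3 = 63 to 66 + 3 = 69.
- With month 66 filled, the next clinic visit is 66 + 6 = 72. The next annual visit is also month 72.
- Month 78 results only from 66 + 12. Neither month 66 nor month 78 is an annual visit, so the annual schedule does not explain the example.

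**2. The value lies outside the window of its label under either version.**
- Month 72 has window 69–75. Month 68 is outside it, and the label is 72 − 68 = 4 months later than the measurement.
- Month 78 has window 75–81. Month 68 is outside it, and the label is 78 − 68 = 10 months later.

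**3. General size of the shift, month-66 visit on time.**
- The forward move applies to an EOS visit between months 66 and 69.
- Under the wording, the shift runs from 72 − 69 = 3 to 72 − 66 = 6 months. If the month-66 visit took place 2 weeks early, the upper end is 72 − 65.5 = 6.5 months.
- Under the example's pattern it is 78 − 69 = 9 to 78 − 66 = 12 months.
- If EOS times are uniform between clinic visits (an assumption), 3/6 = half of them fall in the affected part of the interval.

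**4. What the shift means for one subject's walk distance, assuming linear decline.**

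| Source | 3 months | 6 months |
|---|---|---|
| Fx1B-201 | 11 × 3/12 = 2.75 m | 11 × 6/12 = 5.5 m |
| TRACS | 44 × 3/12 = 11 m | 44 × 6/12 = 22 m |

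The TRACS figures come from the natural-history cohort, so they are the less favourable end of the range.

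**5. Effect on a category percentage.** Assume a row of 10 that includes one mapped record, and let k of the other nine be in the same category. Removing the record changes the percentage by (k + 1)/10 − k/9 = (9 − k)/90. That is 10 points at k = 0 and 4.4 points at k = 5, so 10 points is the maximum.

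**6. After the change.** An EOS visit at month 68 with month 66 filled enters no later scheduled visit, and months 72 and 78 both stay missing. An EOS visit at month 70 with month 72 empty is ordinary windowing (69–75) and is unaffected.

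**The case against.** The best defence is that the sections work in sequence: Appendix 2 first assigns observed records to visits, and Section 7 then leaves every unfilled slot missing. The EOS value is a genuine measurement, used once. This does not remove the conflict, because the slot Appendix 2 fills is still a visit after discontinuation, and Section 7 makes no exception for mapped records.

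Several stronger readings are tempting, and the documents do not support them:

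- **That LOCF has returned.** SAP Section 1 records its removal as inappropriate for this study's discontinuations. LOCF reuses a value already tabulated. Here a separate measurement is entered once, in one slot.
- **That subjects who died are generally tabulated as alive.** This needs a subject who attended an EOS visit and then died before the labelled month. A subject who dies without an EOS visit has no value to move. Time-to-event mortality runs on dates.
- **That the shift reaches 9 months under the wording.** That needs an EOS visit at month 63 with the month-66 slot already filled from the same window, which is practically impossible.
- **That the rule flatters the drug.** The mapped value may understate that subject's own later decline. However, leaving out subjects who are doing badly may make a row look healthier. Nor does leaving mean failing: Protocol 6.3 counts subjects who move to prescription tafamidis as completers.

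It also stands that SAP 4.1 sets no formal hypotheses, so no test or decision rule turns on this.

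**Conclusion.** The contradiction is real and should be reconciled. It is limited to discontinued subjects whose EOS visit falls in a filled window, with at most one later visit per subject. The example adds a separate error, since month 78 is not the next clinic visit after month 66.

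The per-subject sizes rest on on-time clinic visits and linear decline, and the figure of up to 10 percentage points rests on an assumed row of 10. The supportable conclusion is that some values will carry the wrong visit label and that the SAP gives two answers for the same cell. The documents do not show which way row means would move.

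**What to change.** Make Appendix 2 agree with Section 7:

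- Assign an early-termination value to a scheduled visit only if it falls within that visit's own ±3-month window and the slot is empty.
- Otherwise show it in a separate end-of-study row and in the listing with its actual study day, and leave all later scheduled visits missing in the tables and the model.
- Delete the month-78 example or correct it to match the revised rule.

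The cost is about one SAP sentence and a change to the visit-mapping program. The downside is that EOS values whose slot is filled no longer enter the visit-based MMRM, which loses a last measurement before dropout that a likelihood-based model can use. A sensitivity run that includes these values at their actual time would address this with data already collected.

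### SAP Appendix 2's end-of-study example sends month 68 to month 78 where its own rule gives month 72; separately, the SAP 8.1.1 change-from-baseline model names no time term

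*SAP*

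**What the plan says.** **Visit mapping.** SAP Appendix 2 widens each clinic visit window to 3 months either side of the scheduled month. If an early-termination visit lands in a window that already holds a visit, "then the EOS visit should be mapped forward to the next clinic visit". The example that follows puts the EOS visit at month 68. With no month 66 visit it becomes month 66; otherwise, "If there is a month 66 visit, then the EOS visit becomes the month 78 visit".

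Unscheduled visits have a differently worded rule: they are "mapped forward to the next appropriate visit for that measure if that visit is available". That example opens: "As an example, the unscheduled visit occurs at month 68 and the data are collected annually". It too uses months 66 and 78.

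Protocol 6.2 lists clinic visits under the heading "6.2.2. Months 6, 12, 18, 24, 30, 36, 42, 48, 54, 60, 66, 72, 78, 84, 90, 96, 102, 108, 114" and the added ECG and echocardiogram under "6.2.3. Months 12, 24, 36, 48, 60, 72, 84, 96, 108".

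**Model.** SAP 8.1.1 gives adjusted means, standard errors and 95% confidence intervals for change from baseline from an MMRM, whose listed terms are a random subject effect and baseline. SAP 6.6 adds disease duration where appropriate. SAP 8.2 applies 8.1.1 to the KCCQ, 6-minute walk, echocardiography and the cardiac biomarkers. For the KCCQ, Protocol 9.2.4 specifies baseline, a random subject effect and a fixed effect of time.

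**The concern.** The mapping rule and its example produce different datasets, and a programmer will often code from the example. The mapping will be used: under Protocol 6.3, subjects who discontinue "will have a final end of study visit performed, including all safety and efficacy assessments, at the time of discontinuation". Following the example puts a leaver's last value in the month-78 row and denominator. At most one EOS value per subject and endpoint is affected. But at most about 35 subjects enrol (Protocol 9.1), and SAP 8.1.2 itself expects numbers to fall, so late rows are small.

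The missing time term matters because a model without one yields an adjusted mean that belongs to no stated time point. SAP 6.1 lists KCCQ and 6-minute walk at each visit, so a reader would expect adjusted change by visit.

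**Working it through.** **Part 1: where does month 68 go?**

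Inputs: clinic months 6 to 114 by 6 (Protocol 6.2.2); annual months 12 to 108 by 12 (Protocol 6.2.3); clinic windows of ±3 months (SAP Appendix 2).

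- Windows: month 66 covers 63–69, month 72 covers 69–75, month 78 covers 75–81. Month 68 lies only in the month-66 window.
- Next clinic visit after 66: 66 + 6 = 72. The SAP example's figure, 78, is not reproduced.
- Label minus measurement: 72 − 68 = 4 months by the rule; 78 − 68 = 10 months by the example. The month-78 window opens 75 − 68 = 7 months after the assessment.
- In general, for an EOS visit d months after the nominal month of a filled visit, with 0 < d < 3: the rule's lag is 6 − d, between 3 and 6 months. If the example's 12-month step is generalised, the lag is 12 − d, between 9 and 12 months.
- At the end of the schedule, with month 114 filled and an EOS visit between 114 and 117, that step gives 114 + 12 = 126, beyond the 120-month maximum.

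Two readings might rescue 78; neither does.

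- *Annual data.* The EOS example carries no such qualifier. On the annual schedule (60, 72, 84) the next visit after 66 is again 72, and neither 66 nor 78 is an annual visit.
- *Parent-study clock.* Appendix 2 fixes the clock: "For the purpose of this study, Day 1 is defined as the first dose day under this protocol". Counting from Fx1B-201, 12 months earlier, adds 12 to every month. Months 66, 72 and 78 stay on the 6-monthly list, 60, 72 and 84 stay on the annual list, and 66 and 78 stay off it.

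The unscheduled-visit example does not contradict its own rule in the same way, because that rule refers to the next appropriate visit for the measure. But it is written for annual data and uses two months at which no annual assessment is scheduled. Appendix 2 also gives no window specific to annual measures. If the ±3-month clinic window is used, month 60 covers 57–63 and month 72 covers 69–75, so an annual measure taken at month 68 falls in neither.

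**Part 2: what does the listed model estimate?**

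| Term | Protocol 9.2.4 (KCCQ) | SAP 8.1.1 and 6.6 |
|---|---|---|
| Baseline | yes | yes |
| Random subject effect | yes | yes |
| Time | fixed effect | not named |
| Disease duration | no | where appropriate |

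- With no time term there is one adjusted mean per endpoint. Scheduled Fx1B-303 clinic visits number 114/6 = 19 (KCCQ, walk, biomarkers); annual visits number 108/12 = 9 (echocardiography). Parent-study visits come on top.
- For the 10 KCCQ scores: 10 adjusted means instead of 10 × 19 = 190 over the Fx1B-303 visits.
- Span pooled: 1 year in Fx1B-201 plus up to 10 years = 11 years.

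A simulation shows the consequence. Its inputs are assumptions, not document figures: 31 subjects, 6-monthly visits to month 60, a true decline of 3 points per year, between-subject and residual SD of 8, and 40 simulated trials per row.

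| Dropout per visit | No time term: single mean | With visit: month 6 | With visit: month 60 |
|---|---|---|---|
| 0% | −8.6 | −1.8 | −15.3 |
| 5% | −6.9 | −1.5 | −14.7 |
| 10% | −5.8 | −1.4 | −14.8 |

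The true changes are −3 × 0.5 = −1.5 at month 6 and −3 × 5 = −15 at month 60. The model with visit recovers both, up to simulation error. The pooled mean depends on how long subjects stay, although the decline is the same in every row.

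**The case against.** On mapping, the other side concedes that 78 does not fit the rule but calls it a wrong number beneath a clear instruction. Several points stand. The SAP never states a 12-month step, so the 9–12 month range and month 126 follow only if the example is generalised. The lag ranges assume the EOS visit falls after the nominal month; clinic visits may be up to 2 weeks early, and the lags can then slightly exceed 6 and 12. Month 72 is itself later than the month-68 departure, so the error beyond what the rule already accepts is 78 − 72 = 6 months. The ±3-month clinic window can be read as covering annual measures, since these are done at clinic visits.

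On the model, an MMRM conventionally includes visit, so this may be incomplete wording, and the single-mean result is the literal reading. Protocol 9.2.4 says time, not categorical visit, and does not ask for adjusted means by visit. With at most about 35 subjects and 19 or more visit levels, late estimates will be imprecise. Unadjusted by-visit summaries meet the endpoint list in SAP 6.1 and are unaffected. For endpoints other than the KCCQ the protocol names no model.

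These points limit the size of the finding; they do not remove it. The protocol lets the SAP modify its plans, but the SAP's amendment log records no removal of time, and one entry says that 6.1 and 8.2 were aligned with the protocol. That points to an omission.

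**Conclusion.** Both parts hold. The EOS example contradicts the rule it illustrates: the rule gives month 72, the example month 78, a label 10 months late instead of 4. The effect on any visit mean depends on how leavers compare with those who remain, which the documents do not give, so none is claimed.

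As written, the SAP 8.1.1 model lacks the time effect that the protocol specifies for the KCCQ. For the other continuous endpoints this is a gap in the SAP, not a conflict with the protocol. The counts of lost by-visit means assume the model is fitted exactly as listed.

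The study is descriptive with no hypothesis tests (SAP 4.1), so the consequence is limited to visit-level estimates. Both should be corrected.

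**What to change.** In SAP Appendix 2:

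- Change 78 to 72 in the EOS example.
- Rewrite the unscheduled-visit example on the 60/72/84 annual schedule, and state the window for annual measures, even if it is the clinic window.
- Optionally, add that an EOS value mapped forward is observed data taken at discontinuation, so the SAP section 7 rule that later visits stay missing does not remove it.

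In SAP 8.1.1, add visit (time) as a fixed effect, keep the random subject intercept, and report adjusted means with standard errors and confidence intervals by visit. Stating that visit is categorical would settle the ambiguity in the protocol's term.

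The cost is SAP wording and the programming specification. No new data are needed.
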